## 2.2. Conclusions on Toxicity Findings

## 2.3. Clinical Studies

### 2.3.1. Seborrheic Dermatitis Phase 2a

ARQ-154-203 (NCT 04091646) was a Phase 2a, parallel group, double blind, vehicle-controlled study that evaluated ARQ-154 foam 0.3% for the treatment of seborrheic dermatitis involving the scalp, face, and/or body. ARQ-154 foam 0.3% or matching vehicle was applied once daily (QD) for eight weeks to adult subjects with a minimum Investigator Global Assessment (IGA) of moderate (IGA of 3 on a 5-point scale from 0 to 4). A total of 226 subjects were randomized at a ratio of 2:1 to receive ARQ-154 foam 0.3% or matching vehicle foam. All randomized subjects were included in both the safety and intent-to-treat (ITT) populations.

The study demonstrated that ARQ-154 foam 0.3% was highly efficacious (including early timepoints), safe, and well-tolerated following once-daily topical application in subjects with moderate to severe seborrheic dermatitis. The study's primary endpoint was IGA Success, defined as achievement of an IGA score of 'clear' or 'almost clear' PLUS a 2-grade improvement from Baseline at Week 8. This endpoint was met with IGA success in 73.8% of subjects in the ARQ-154 treatment group vs. 40.9% of vehicle-treated subjects ( $p<0.0001$ ). IGA success was greater with ARQ-154 than vehicle starting at the first post-baseline visit at Week 2 (33.8% of ARQ-154 vs 14.5% of vehicle subjects,  $p=0.0029$ ). Worst Itch-Numeric Rating Scale (WI-NRS) success at Week 8, defined as a  $\geq 4$ -point improvement from Baseline was 64.6% for ARQ-154 vs. 33.3% for vehicle ( $p=0.0006$ ), with statistical significance as early as Week 2 (52.8% for ARQ-154 vs 22.8% for vehicle,  $p=0.0005$ ).

ARQ-154 foam 0.3% was safe and demonstrated excellent tolerability based on adverse event (AE) reporting and both investigator-rated and subject-rated local tolerability assessments. No serious adverse events (SAEs) were reported, and only a few subjects reported treatment-related adverse events (TEAEs) (1.9% with ARQ-154 and 4.2% with vehicle) or discontinued study drug due to AEs (1.3% with ARQ-154 and 2.8% with vehicle). Most ( $>90\%$ ) TEAEs were grade 1 or grade 2, i.e., mild or moderate. Systemic exposure to roflumilast and roflumilast N-oxide in subjects with seborrheic dermatitis treated with ARQ-154 foam 0.3% appeared comparable to that of subjects with psoriasis treated with ARQ-151 cream 0.3%, when adjusted for body surface area (BSA).

## 2.4. Rationale for Development

The development plan for ARQ-154 foam will leverage experience to date with ARQ-151 cream, which has been safe, well tolerated, and effective in multiple Phase 2 studies for the treatment of plaque psoriasis or atopic dermatitis. Given the unmet need for new medical therapies for seborrheic dermatitis and the results of a phase 2a study of ARQ-154 foam 0.3% in seborrheic

dermatitis, the Sponsor is pursuing development of ARQ-154 foam 0.3% for the treatment of seborrheic dermatitis in this phase 3 study. Relative to topical formulations such as a cream or gel, the foam formulation in the present study is expected to be well suited for the treatment of the scalp, where seborrheic dermatitis may predominate.

#### **2.4.1. Dose Selection**

ARQ-154 foam at 0.3% was selected for this study to match the dose of ARQ-154 foam from the phase 2a study ARQ-154-203. The 0.3% dose is also consistent with the dose of the related roflumilast cream formulation (ARQ-151 cream 0.3%) which is being evaluated in phase 3 for plaque psoriasis. The 0.3% dose for ARQ-151 cream was selected based on results of the phase 2b study plaque psoriasis study ARQ-151-201, in which the 0.3% concentration demonstrated greater efficacy than the 0.15% concentration. In that phase 2b study, there were no differences in the safety profiles of the two doses, supporting that it was not necessary to evaluate doses less than 0.3% in seborrheic dermatitis. The Sponsor expects similar doses to be safe and effective in seborrheic dermatitis, as supported by the phase 2a seborrheic dermatitis study ARQ-154-203. Additionally, many cases of seborrheic dermatitis may be challenging to treat or refractory to standard treatment (particularly in patients with neurologic conditions, as included here) and the Sponsor is targeting greater efficacy than commonly used topical antifungals and low potency steroids, further supporting the choice to evaluate the 0.3% dose.

Consistent with the close similarities between ARQ-151 and ARQ-154 formulations, study ARQ-154-203 demonstrated comparable pharmacokinetics with ARQ-154 foam as have been described with ARQ-151 cream. Additionally, pharmacokinetics in seborrheic dermatitis appeared comparable to those seen in plaque psoriasis and atopic dermatitis.

#### **2.4.2. Risks and/or Benefits to Subjects**

Based on efficacy data from subjects randomized to active treatment group of the phase 2a study ARQ-154-203, including at Week 2, it is expected that subjects in the present study ARQ-154-304 will experience improvement in their seborrheic dermatitis. Subjects randomized to the vehicle treatment group may also see some improvement as the formulation of ARQ-154 may have a moisturizing effect.

The safety monitoring practices employed in this protocol (i.e., physical examinations, vital signs/weight, local skin toleration assessments, hematology, serum chemistry, urinalysis, PHQ-8/PHQ-A/CDI-2, C-SSRS and AE questioning) are adequate to protect the subjects' safety and should detect expected AEs. The lack of nausea and vomiting seen in ARQ-151 cream and ARQ-154 foam studies to date may be related to the lack of 'peak to trough'  $C_{max}$  variation, lower  $C_{max}$  values than observed following oral administration, or bypassing of the gastrointestinal tract with topical administration.

Oral roflumilast has now been used for almost a decade in the treatment of COPD exacerbations and its safety record has been well-documented. The known adverse effects of oral treatment in the COPD population (nausea, diarrhea, weight loss, psychiatric AEs) are readily monitored as specific in this protocol. The current protocol is designed to detect these adverse events and others should they occur, and provides guidance for management, as necessary, to ensure patient safety. Furthermore, the safety profiles of ARQ-151 and ARQ-154 at doses ranging from

0.15% to 0.5% in the preceding studies in seborrheic dermatitis and psoriasis suggests that ARQ-154 foam 0.3% will be similarly safe and well tolerated in the present study.

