### 1.3. Schedule of Visits and Assessments

Study Procedure	Screen	Baseline Day 0	Week 2 Day 14	Week 4 Day 28	Week 8 a Day 56
Visit	1	2	3	4	5
Visit Window	-4 weeks		± 3 days	± 5 days	± 5 days
Informed consent/assent	X				
Medical/surgical history, demography	X				
Physical examination b	X	X			X
Fitzpatrick Skin Type	X				
I/E criteria	X	X			
Randomization		X			
Hematology, Chemistry, and Urinalysis c	X	X		X	X
Vital signs, weight, height d	X	X	X	X	X
IGA, Overall Assessment of Erythema, Overall Assessment of Scaling e	X	X	X	X	X
BSA f	X	X	X	X	X
DLQI/CDLQI g , Scalpdex	X	X	X	X	X
Daily WI-NRS h at home (non-clinic)			Day -7 through Day 56		
Local Tolerability Assessment i		X		X	X
Pigmentation Assessment j	X	X	X	X	X
C-SSRS, CDI-2/PHQ-8/PHQ-A k	X	X		X	X
Medical Photography l		X	X	X	X
Serum pregnancy test m	X				
Urine pregnancy test n		X		X	X
PK sampling o				X	X
IP application and subject/family training p		X	X		
Dispense investigational product kit q		X	X	X	
Dispense / review dosing diary		X	X	X	X
Weigh investigational product r		X	X	X	X
Compliance calculation s			X	X	X
Adverse event assessment t		X	X	X	X
Prior & Concomitant medications	X	X	X	X	X

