## **4. INVESTIGATIONAL PLAN**

### **4.1. Overall Study Design and Plan**

This is a phase 3, parallel group, double blind, vehicle-controlled study in which ARQ-154 foam 0.3% or vehicle foam is applied QD x 8 weeks to subjects 9 years of age and older with at least moderate seborrheic dermatitis affecting the scalp and/or rest of body.

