### 4.8.2. Treatment Administration

Initial treatment with the IP will occur on Day 0. At the randomization visit (Baseline), the study staff will demonstrate to the subject how to apply ARQ-154 foam 0.3% or vehicle foam using the first canister from the kit that is assigned to the subject at randomization. Study site staff will be trained to ensure a proper amount is dispensed from the foam can and applied to seborrheic dermatitis lesion(s) as a thin film and rubbed in thoroughly but gently, until the ‘white’ has disappeared. **For scalp lesions, special attention should be given to ensuring adequate investigational product is applied to scalp skin and not rubbed off on hair.** The subject will then practice dispensing a similar amount of investigational product and applying to seborrheic dermatitis lesion(s). The study staff will confirm that the subject’s application technique is correct.

Subjects will be instructed to apply IP QD in the evening (except at Baseline and Week 2, in which case IP will be applied at the study site) to areas of seborrheic dermatitis lesions identified by the Investigator at Baseline using a Body and Scalp Diagram (see [Appendix 1](#)). IP will be applied at least 20 minutes before going to bed.

For Scalp Lesions: IP will be applied when the skin and hair on the scalp is dry. Subjects should dispense IP on their fingers, then part hair where there are lesions and rub IP into scalp skin. As the IP is applied, the subject should move any hair away to ensure that sufficient foam is applied directly to the affected skin on the scalp. Subjects should not use other hair products for at least an hour before or after application.

For Non-scalp Lesions: IP should be applied to affected areas as a thin layer and rubbed in thoroughly but gently until the foam has disappeared.

Subjects should not wash areas (or otherwise expose to water, e.g., swimming) where ARQ-154 foam or vehicle has been applied until at least 4 hours after IP application and preferably not until the following morning.

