## APPENDIX 2. PATIENT HEALTH QUESTIONNAIRE DEPRESSION SCALE (PHQ-8)

Over the **last 2 weeks**, how often have you been bothered by any of the following problems?  
(circle **one** number on each line)

How often during the past 2 weeks were you bothered by...	Not at all	Several days	More than half the days	Nearly every day
1. Little interest or pleasure in doing things .....	0	1	2	3
2. Feeling down, depressed, or hopeless.....	0	1	2	3
3. Trouble falling or staying asleep, or sleeping too much .....	0	1	2	3
4. Feeling tired or having little energy.....	0	1	2	3
5. Poor appetite or overeating .....	0	1	2	3
6. Feeling bad about yourself, or that you are a failure, or have let yourself or your family down.....	0	1	2	3
7. Trouble concentrating on things, such as reading the newspaper or watching television.....	0	1	2	3
8. Moving or speaking so slowly that other people could have noticed. Or the opposite – being so fidgety or restless that you have been moving around a lot more than usual .....	0	1	2	3

**APPENDIX 3. MODIFIED PATIENT HEALTH QUESTIONNAIRE  
DEPRESSION SCALE (PHQ-A)**

**Instructions:** How often have you been bothered by each of the following symptoms during the past two weeks? For each symptom put an "X" in the box beneath the answer that best describes how you have been feeling.

	(0) Not at all	(1) Several days	(2) More than half the days	(3) Nearly every day
1. Feeling down, depressed, irritable, or hopeless?				
2. Little interest or pleasure in doing things?				
3. Trouble falling asleep, staying asleep, or sleeping too much?				
4. Poor appetite, weight loss, or overeating?				
5. Feeling tired, or having little energy?				
6. Feeling bad about yourself – or feeling that you are a failure, or that you have let yourself or your family down?				
7. Trouble concentrating on things like school work, reading, or watching TV?				
8. Moving or speaking so slowly that other people could have noticed?  Or the opposite – being so fidgety or restless that you were moving around a lot more than usual?				

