**Instructions:**  
For each of the statements below, select one response that best describes your observations of your child in the past two weeks.  
Indicate your response for each item by circling the number that best corresponds to your choice. You may change an item response by drawing an 'X' through your original choice and selecting a new response.  
Remember, for each statement, pick one answer that best describes your observations of your child in the PAST TWO WEEKS.

My child	Not at all	Some of the time	Often	Much or most of the time
1. looks sad.	0	1	2	3
2. has wt.	0	1	2	3
3. does not like himself or herself.	0	1	2	3
4. blames himself or herself or others.	0	1	2	3
5. cries or looks tearful.	0	1	2	3
6. is cranky or irritable.	0	1	2	3
7. enjoys being with people.	0	1	2	3
8. thinks that he or she is ugly.	0	1	2	3
9. has to push himself or herself to do schoolwork.	0	1	2	3
10. has trouble sleeping at night.	0	1	2	3
11. looks tired or fatigued.	0	1	2	3
12. seems lonely.	0	1	2	3
13. enjoys school.	0	1	2	3
14. spends time with friends.	0	1	2	3
15. is showing worse school performance than before.	0	1	2	3
16. does what he or she is told.	0	1	2	3
17. has disagreements and conflicts with others.	0	1	2	3

Copyright © 2013 [name] and Multi Health Systems Inc. All rights reserved.  
In the United States, [name]. [name]. In Canada, [name].  
[name], [name]. [contact] (internationally), [contact]. [contact] or [name].

**APPENDIX 5. COLUMBIA-SUICIDE SEVERITY RATING SCALE  
(C-SSRS) BASELINE/SCREENING VERSION**

**COLUMBIA-SUICIDE SEVERITY  
RATING SCALE  
(C-SSRS)**

Baseline/Screening Version

Version 1/14/09

***Posner, K.; Brent, D.; Lucas, C.; Gould, M.; Stanley, B.; Brown, G.; Fisher, P.; Zelazny, J.;  
Burke, A.; Oquendo, M.; Mann, J.***

*Disclaimer:*

*This scale is intended to be used by individuals who have received training in its administration. The questions contained in the Columbia-Suicide Severity Rating Scale are suggested probes. Ultimately, the determination of the presence of suicidal ideation or behavior depends on the judgment of the individual administering the scale.*

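### Scheduled PHQ-8, PHQ-A and CDI-2 forms look back over only about half of the dosing days and miss the first two weeks; adding them at the existing Week 2 visit is a cheap improvement

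*Protocol*

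**What the plan says.** Protocol 2.4.2 lists the known effects of the oral drug, psychiatric events included, and says: "psychiatric AEs) are readily monitored as specific in this protocol". The paragraph before it judges a whole set of practices adequate. The depression scales, the C-SSRS and AE questioning are all part of that set.

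Dosing: "Initial treatment with the IP will occur on Day 0" (Protocol 4.8.2), and the product "is applied QD x 8 weeks to subjects 9 years of age and older" (Protocol 4.1).

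Timing: in Protocol 1.3 the row "C-SSRS, CDI-2/PHQ-8/PHQ-A" is marked at Screening, Baseline, Week 4 and Week 8. The Week 2 cell is blank. SAP Table 1 has the same pattern.

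Recall is built into each form:
- PHQ-8 (Protocol Appendix 2): "How often during the past 2 weeks were you bothered by"
- Modified PHQ-A (Protocol Appendix 3): "How often have you been bothered by each of the following symptoms during the past two weeks"
- CDI-2 parent report (Protocol Appendix 4): "pick one answer that best describes your observations of your child in the PAST TWO WEEKS"

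SAP 9.5 and 9.6 summarise these scores by time point, in planned tables 14.3.5 (PHQ shift) and 14.3.6 (CDI-2).

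**The concern.** A form with a fixed two-week look-back cannot reach further back because the previous visit was longer ago. The Week 4 form says nothing about the first two weeks of dosing, and the Week 8 form says nothing about the two weeks after Week 4. Weight loss, named in the same sentence of 2.4.2, is checked at every visit including Week 2 (Protocol 1.3, footnote d). The depression scales are not, and no reason is given.

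Two things are at stake. The referral and interruption steps in Protocol 5.1.7-5.1.9 and part of 5.9 are triggered by scores, so an episode that falls between look-back periods triggers none of them. And a reader of tables 14.3.5 and 14.3.6 could take an absence of shifts as describing all eight weeks, because neither document says which days the scores cover.

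**Working it through.** The documents state no coverage figure, so there is none to reproduce. The check is a count of days.

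**Inputs**
- Dosing runs from Day 0 to the Week 8 visit: Days 0-55 if that visit is on Day 56 (Protocol 4.1, 4.8.2).
- Look-back is 14 days for all three scales (Appendices 2-4).
- Windows: Week 2 = Day 14 ± 3 (Days 11-17), Week 4 = Day 28 ± 5 (Days 23-33), Week 8 = Day 56 ± 5 (Days 51-61) (Protocol 1.3).

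**Formula.** A form given on Day v covers Days v-14 to v-1. Coverage = distinct dosing days covered ÷ day of the Week 8 visit.

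**Current schedule, nominal visits**
- Week 4 (Day 28) covers Days 14-27; Week 8 (Day 56) covers Days 42-55.
- Coverage = (14 + 14) / 56 = 28/56 = 50%.
- Not covered: Days 0-13 and Days 28-41.

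**Current schedule, allowed windows**
- The latest Week 4 visit covers up to Day 32 and the earliest Week 8 visit starts at 51 - 14 = Day 37. The two look-backs never overlap, so 28 days are always covered.
- Week 8 on Day 51: 28/51 = 55%. Week 8 on Day 61: 28/61 = 46%.
- First covered day: 23 - 14 = Day 9 at the earliest, 33 - 14 = Day 19 at the latest. Days 0-8 are never reached. At best 5 of the first 14 days (Days 9-13) are.
- In the second gap, Days 33-36 are never reached.

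**With a form at Week 2**

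| Visit days (Weeks 2, 4, 8) | Days covered | Coverage |
|---|---|---|
| 14, 28, 56 (nominal) | 0-27 and 42-55 | 42/56 = 75% |
| 14, 28, 51 (highest) | 0-27 and 37-50 | 42/51 = 82% |
| 17, 23, 61 (lowest) | 3-22 and 47-60 | 34/61 = 56% |

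At least 11 of the first 14 days are then covered: Week 2 on Day 11 covers Days 0-10, and Week 2 on Day 17 covers Days 3-16. Days 28-41 stay uncovered nominally, because no clinic visit lies between Weeks 4 and 8.

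**What else reaches the gaps**

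| Channel | Who | Reach | What it picks up |
|---|---|---|---|
| C-SSRS, Since Last Visit form (Protocol 5.1.10) | Age 12 and older | Whole interval before Weeks 4 and 8 | Suicidal ideation and behavior |
| Open AE question and diary review (4.8.3, 5.7.4) | All | Every visit, including Week 2 | Whatever is reported or written down |
| Early termination visit (1.3 footnote a; 5.5) | Withdrawn subjects, unless consent is withdrawn | Two weeks before that visit | The depression scales themselves |

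Subjects aged 9-11 have no C-SSRS, so the CDI-2 is their only structured psychiatric instrument.

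**The case against.** The strongest reply is that 2.4.2 claims adequacy for the whole set of practices, not continuous coverage by one scale, and that the set does span the gaps. That stands: the quoted sentence is not contradicted. Three stronger readings that a reader might infer are not supported.

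- *An early dropout leaves no score.* Subjects who terminate early are asked back for the Week 8 assessments, which include the scales. SAP 6.1.5 and Table 2 place an early termination measurement in the Week 2 window (Days 2-22) when no scheduled one exists. A subject leaving around Day 10 who attends would be asked about all of the dosing so far. The exceptions are withdrawal of consent and failure to attend.
- *The open AE question is the only net left.* The C-SSRS and the diary also reach the gaps. Investigators may add safety assessments (Protocol 5.1) or unscheduled visits (5.6). Protocol 5.9 provides for referral for suicidality and for Medical Monitor contact about events of concern without any PHQ or CDI-2 score.
- *Every episode that starts in a gap is missed.* One that lasts into Days 14-27 or 42-55 falls within the next form's look-back.

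It can also be said that the documents show no early-onset signal. The phase 2a study reported no SAEs and treatment-related AEs in 1.9% on active against 4.2% on vehicle (Protocol 2.3.1), and the entry criteria exclude raised depression scores and any lifetime suicidality (4.5.2). That limits how many episodes to expect, but it does not change which days the scores describe. Finally, a Week 2 form leaves the second gap open, and in the least favorable visit timing coverage reaches only 56%. Both are true. The gain is mainly in the first two weeks.

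**Conclusion.** The point holds in a limited form, as a low-cost improvement and not as an inconsistency in the plan. Scheduled depression scoring looks back over 28 of 56 dosing days (50% nominal, 46-55% across windows), and Days 0-8 are outside it under any allowed timing. What can go unscored is a non-suicidal depressive episode that resolves within a gap in a subject who remains in the study. The exposure is greatest at ages 9-11.

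The count assumes a look-back of exactly 14 days ending the day before the visit, dosing up to the Week 8 visit, and visits inside their windows. The documents give no rate of short depressive episodes, so the number that might be missed cannot be estimated.

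**What to change.** For this protocol or any reuse of it: give the age-appropriate scale (PHQ-8, modified PHQ-A or CDI-2) at the existing Week 2 visit, mark it in Protocol 1.3 and SAP Table 1, and show Week 2 in tables 14.3.5 and 14.3.6. Add a footnote to those tables stating which dosing days the scores describe, since Days 28-41 remain uncovered nominally. Action thresholds and clinical rules stay as they are.

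The cost is one 8-item form, or the 17-item parent form, at a visit that already takes place: a few minutes per subject and one more table column. Protocol Appendix 11 already allows these scales to be collected remotely, so a missed clinic visit need not mean a missed form.

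For subjects already treated, no Week 2 form can be added: SAP Section 1 gives database lock as 17-May-2022. There, the footnote to tables 14.3.5 and 14.3.6 is the only change available.

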### **3. STUDY OBJECTIVES AND ENDPOINTS**

#### **3.1. Study Objectives**

##### **3.1.1. Primary Objective**

The primary objective of this study is to assess the safety and efficacy of ARQ-154 foam 0.3% administered once daily (QD) vs vehicle foam for 8 weeks in subjects with seborrheic dermatitis.

#### **3.2. Study Endpoints**

##### **3.2.1. Primary Endpoint**

The primary efficacy endpoint in this study is success in Investigator Global Assessment (IGA) of disease severity, defined as an IGA score of ‘clear’ or ‘almost clear’ plus a 2-point improvement at Week 8.

##### **3.2.2. Secondary Endpoints**

The Secondary Efficacy Endpoints will include:

- In subjects with a Baseline WI-NRS pruritus score of  $\geq 4$ , achievement of a  $\geq 4$ -point improvement from Baseline in WI-NRS pruritus score at Week 8 (“WI-NRS Success at Week 8”)
- WI-NRS Success at Week 4
- WI-NRS Success at Week 2
- IGA Success at Week 4
- Achievement of an Overall Assessment of Scaling (0-3 scale) score of 0 at Week 8
- Achievement of an Overall Assessment of Erythema (0-3 scale) score of 0 at Week 8
- Achievement of an IGA score of ‘clear’ at Week 8
- IGA Success at Week 2

Additional exploratory endpoints will be included in the SAP.

## **4. INVESTIGATIONAL PLAN**

### **4.1. Overall Study Design and Plan**

This is a phase 3, parallel group, double blind, vehicle-controlled study in which ARQ-154 foam 0.3% or vehicle foam is applied QD x 8 weeks to subjects 9 years of age and older with at least moderate seborrheic dermatitis affecting the scalp and/or rest of body.

### **4.2. Number of Sites and Subjects**

A total of up to approximately 450 subjects will be enrolled at approximately 50 study sites in North America. Additional countries or study sites may be added, as necessary. Subjects will be male and female children (9 - 11 y/o), adolescents (12 - 17 y/o) and adults ( $\geq 18$  y/o). Subjects will have an IGA of disease severity of at least Moderate ('3') at Baseline. Subjects must have no more than 20% BSA of seborrheic dermatitis. All lesions on a subject will be treated including the scalp, face, trunk, and intertriginous areas.

